heterogeneity, they result in an unfortunate reality, namely that the populations most likely to have and to transmit TB are also the populations (young adult, male, poor) that are hardest to reach through existing interventions that rely on the routine healthcare system. A hallmark of these high-TB-risk demographic groups is their high level of mobility and migration. While the motivations for human movement are diverse, two major patterns include migration to urban centers for employment and return to homelands to spend time with families. Such mobility is common in many developing country settings,^{24,25} and can result in temporary population spikes in "destination" areas of 125%.²⁶ South Africa is emblematic of these patterns, with a recent net population shift from rural to urban areas,²⁷ a population of temporary migrants overwhelmingly comprised of males age 20-45 years.²⁸ and the majority of its tourism representing trips for visiting family and relatives.²⁹ Internal migration has been linked with HIV (a major risk factor for TB): in KwaZulu Natal, South Africa, the prevalence ratio for HIV, comparing migrants to non-migrants in the same neighborhood, was 1.65 and increased with the number of moves.³⁰ Recent migrants are less likely to utilize health services in South Africa,³¹ and are at higher risk of all-cause mortality as well as mortality due specifically to HIV/TB.³² Recent studies have shown that migration likely plays an important role in the transmission of extensively drug resistant TB (XDR-TB)—among 1084 genomically linked casepairs in KwaZulu Natal, the median distance between case-pairs was 108 km, and half of all case-pairs resided in Durban, the urban center of the province, while the other half resided in rural areas.³³ Finally, studies from China and Tajikistan show that migrants are less likely to be appropriately treated for TB, and at higher risk for loss from care, treatment failure and death than non-migrant counterparts.^{34,35} Given the strong demographic correlation between mobility and TB disease risk, co-location of major TB risk factors (e.g., HIV) among migrants, and poorer TB treatment outcomes associated with migration, better understanding of the spatial and temporal dynamics of TB transmission - including the design of effective interventions - among highly mobile populations will be essential if we are to make substantive progress toward ending TB in high-burden settings. In South Africa, which bears the fifth-largest burden of incident TB in the world, household contact investigation is recommended as a key component of the national TB strategic plan for HIV, TB, and sexually transmitted infections.³⁶ Household contact investigation entails visits by healthcare workers to the homes of individuals diagnosed with TB, in order to identify household members who may have TB infection or disease.³⁷ As high-burden countries pursue increasingly ambitious goals for ending TB, the importance of household contact investigation is likely to increase worldwide.³⁸ Furthermore, household contact investigation provides an ideal opportunity to offer HIV counseling and testing.³⁹ However, the practice of household contact investigation also presents both logistical and ethical challenges. For example, one must weigh the deontological value of protecting confidentiality to prevent stigma and blame of the individual diagnosed with TB against the utilitarian perspective of protecting the household and broader community health against infection.⁴⁰ Our unique research collaboration can provide novel insights into migration and TB transmission. To better understand the interplay between mobility and TB transmission, it is important to compare patterns of TB disease and transmission in representative rural and urban settings. Our research infrastructure is ideally placed to make this comparison. Specifically, for

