4 STUDY DESIGN

In this study, we will evaluate two innovative approaches to household contact investigation, namely holiday-time contact investigation in a largely rural province (Limpopo) and evening-time contact investigation in a peri-urban township (Soshanguve in Gauteng province and surrounding areas within North West province). These approaches leverage known patterns of movement and migration in sub-Saharan Africa and throughout the world, namely that younger working individuals (i.e., those at greatest risk of TB and TB transmission) often immigrate from rural to urban areas, spending evenings after work in their urban homes, and returning to their rural family homesteads for major holidays. We will compare each of these approaches to each other and to standard household contact investigation during business hours from 8 am to 4 pm Monday through Friday in each setting, with a primary outcome of the number of additional cases of TB identified per index case and secondary outcomes of implementation, cost-effectiveness and transmission, thus identifying feasible strategies that can be more efficient (per dollar invested) in finding additional cases of TB.

We propose to conduct a four-arm parallel randomized trial, using the following strategies (See study schematic below):

- 1. **Routine contact investigation in rural Limpopo**. Study staff will perform routine contact investigation of TB cases diagnosed in study hospitals in Limpopo, throughout the year. Contact investigation will be performed on weekdays during business hours.
- 2. Holiday contact investigation in rural Limpopo. At the time of diagnosis, study staff will ask TB cases diagnosed in Limpopo study hospitals for consent to perform deferred household contact investigation over a three week period during the Easter holiday (for cases diagnosed between January 1 and Easter) or a five week period during the Christmas holiday (for cases diagnosed between Easter and December 31). These holiday periods will align with the public school holidays in South Africa as detailed by the National Education Policy Act School Calendar.
- 3. **Routine contact investigation in urban Soshanguve and surrounding areas**. Study staff will perform routine contact investigation of TB cases diagnosed in study clinics in Soshanguve, throughout the year. Contact investigation will be performed on weekdays during business hours.

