Index cases will represent a sample of consecutive consenting individuals diagnosed with pulmonary TB (including microbiological and/or chest x-ray diagnosis) from twelve hospitals in Vhembe and Capricorn Districts of Limpopo, and 33 primary health care clinics and two district hospitals in Soshanguve and surrounding areas. The only exclusion criteria will be a plan not to pursue treatment within the study district (as this would make contact investigation infeasible in the programmatic setting), and being on TB treatment for longer than one month (as these cases will likely be negative by liquid culture in order to identify transmission links between cases using whole genome sequencing). Note that contacts do not have the same requirement of planning to pursue treatment within the district; thus, it is possible - and expected - that holiday contact investigation in Limpopo will yield cases from outside the district, for example. Individuals who later decline to have contact investigation performed (or who, for example, provide false contact information thus making contact investigation infeasible) will still be included in the study sample and in the denominator for all analyses. Our aim is to make the population of this study as representative as possible as the target population for the proposed intervention. Eligible participants in the bioethics sub-study will include all individuals who were enrolled in the parent study and completed follow-up for the primary outcome (including those who declined or were ineligible to participate in household contact investigation). We will enroll consecutive eligible participants in each district until our desired sample size (64 evaluable index cases and 64 evaluable household contacts from each district) has been attained.

Eligibility Criteria

Subjects in each of the below participant categories must meet each eligibility criteria for that category:

TB index cases:

Inclusion criteria:

- Age 0-99 years (Including those recently deceased)
- Diagnosed with pulmonary TB at a study hospital or clinic (microbiological and/or chest x-ray diagnosis)

Exclusion criteria:

- Unwilling/unable to provide informed consent (including next of kin, for those recently deceased)
- Plan not to pursue TB treatment within the study district
- Unwilling/unable to comply with study procedures

Contacts:

Inclusion criteria:

- Age 0-99 years (18-99 for the bioethics sub-study)

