11 STATISTICAL CONSIDERATIONS

11.1 Study Outcome Measures

Primary Outcome Measure:

Our primary effectiveness outcome will be the ratio of the number of secondary TB cases identified and started on treatment per index case, comparing index cases allocated to the novel strategy (off-peak screening in Soshanguve and holiday screening in Limpopo) to those receiving standard contact investigation.

Secondary Outcome Measures:

- The TB prevalence ratio, comparing highly mobile to less mobile individuals, measuring mobility on two scales (neighborhood/intra-urban and regional/intra-national). For the former, we will estimate the number of kilometers traveled on a daily basis (secondary analysis: amount of time spent in transit), truncating long excursions at 50km (one hour).
- 2. TB strain relatedness using maximum likelihood transmission trees. We will integrate TB natural history, epidemiological, and WGS-derived phylogenetic data into a statistical modeling framework to draw probabilistic conclusions about the likelihood of transmission between persons. "Transmitters" will be defined as individuals from whom at least one secondary case most likely originated.
- Relative acceptability of each novel strategy, compared against routine contact investigation. We will measure acceptability of the intervention among index cases and contacts using a short questionnaire given to a randomly selected participant at a randomly selected 15% of the households visited. The interview will cover acceptability of the visit timing, notification, visit activities (TB screening, HIV testing) and study team interaction among others.
- 4. Feasibility of each strategy as the proportion of potentially eligible index cases for whom a household visit was conducted. We will also record all reasons why visits were unable to be conducted (e.g. could not find household, no one ever home, visit not conducted during expected off-peak period).
- 5. Relative fidelity of each novel strategy using a process checklist for each index case and household, including whether the household visit was offered and accepted, whether the visit was attempted, whether the visit was successful (i.e.,

enrolled at least one contact), whether symptom screening and sputum collection were completed and whether newly identified TB cases were notified and referred for treatment.

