1. The TB prevalence ratio, comparing highly mobile to less mobile index patients, measuring mobility on two scales (neighborhood/intra-urban and regional/intra-national). For the former, we will estimate the number of kilometers traveled on a daily basis (secondary analysis: amount of time spent in transit), truncating long excursions at 50km (one hour). Based on exploratory data analysis and consideration of generalizable numbers (e.g., multiples of 5 and 10), we will consider a binary measurement of "highly mobile" versus "less highly mobile" at a natural break near the midpoint of the data. We will then use logbinomial regression to adjust for a priori potential confounders that will include age, sex, socioeconomic status, and HIV status, and robust variance estimation to account for clustering by households. Analyses will be stratified by site. We will perform a similar analysis for regional/intra-national mobility, taking as the primary exposure variable the self-reported number of trips per year greater than 50km (secondary analysis: number of nights spent away from primary residence). For each measure of mobility, we will explore additional methods of modeling the exposure variable, including continuous (linear), using restricted cubic splines (which may yield less interpretable estimates of effect but more flexible incorporation of complex patterns in the data), and as a categorical ("dummy variable") exposure – again at natural breaks in the data.

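### The mobility–TB prevalence ratio pools randomised arms within site with no arm term, and is planned only with adjustment for HIV status

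*Combined protocol and SAP*

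**What the plan says.** All references are to the combined protocol and SAP.

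- **Model (Section 11.4, secondary outcome 1).** TB is regressed on a binary mobility measure by log-binomial regression, with variance robust to household clustering. The model will "adjust for a priori potential confounders that will include age, sex, socioeconomic status, and HIV status". The section adds: "Analyses will be stratified by site". Arm is not mentioned. The binary cut is to be placed at a natural break close to the middle of the data.
- **Population.** Section 11.4 describes the outcome as "The TB prevalence ratio, comparing highly mobile to less mobile index patients". Sections 8.1.2 and 11.1 define the same outcome for individuals, with no restriction to index patients. Index cases qualify by being "Diagnosed with pulmonary TB at a study hospital or clinic (microbiological and/or chest x-ray diagnosis" (Section 5.1).
- **Arms and visit timing.** Section 4 says of the novel strategies: "These approaches leverage known patterns of movement and migration in sub-Saharan Africa and throughout the world". Under Section 7.1, the people eligible as contacts are those in the household when the visit takes place. Section 5.1 expects that "holiday contact investigation in Limpopo will yield cases from outside the district". Routine and off-peak visits are booked within two weeks (Section 6.1); holiday visits wait for Easter or Christmas (Sections 4 and 11.2).
- **HIV.** Section 2.1 calls HIV a major TB risk factor and reports from KwaZulu-Natal that "the prevalence ratio for HIV, comparing migrants to non-migrants in the same neighborhood, was 1.65 and increased with the number of moves".
- **Comparison.** The regression for secondary outcome 8 in Section 11.4 does list study arm among its adjustment variables.

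**The concern.** The arms differ in when the household is visited, and the timing was chosen to reach people who move. Among contacts, arm may therefore be associated with the exposure. Arm may also be associated with detected TB at a given mobility level, for example because disease develops or is diagnosed elsewhere while a holiday visit is pending, or because visitors have been exposed differently from residents. If both associations are present, a model that pools arms reads part of an arm difference as a mobility effect.

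The HIV issue is separate. If mobility raises HIV risk and HIV raises TB risk, an HIV-adjusted ratio leaves out the part of the association that runs through HIV. If HIV is only a confounder, adjustment is right. The plan gives the reader one of the two estimates and does not say which association it is meant to describe.

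At stake is the interpretation of a secondary outcome that bears on the trial's rationale. The randomised primary comparison is unaffected.

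**Working it through.** The plan states no expected ratio, sample size or power for this outcome, so there is no figure to reproduce.

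**Step 1: who can be analysed.** All index patients have TB by inclusion criterion, so TB prevalence among them is 100% in both mobility groups and no informative ratio exists. They are also interviewed before allocation is issued (Section 11.2), so their recorded mobility cannot depend on arm. A workable analysis must include contacts, and that is where arm can matter.

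**Step 2: effect of omitting arm when mobility has no effect.**

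From the plan, per site: 1,600 routine and 800 novel index cases with a mean of two contacts each (Section 11.3), giving 3,200 and 1,600 contacts; 3% TB prevalence in contacts (Section 11.2), used here for the routine arm; a mobility cut near the midpoint, taken as 50% highly mobile overall.

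Assumed, because the plan does not give them: equal numbers of contacts per index case in the two arms, the gap in mobile share between arms, and novel-arm prevalence.

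With n contacts, mobile share m and prevalence p in each arm (p the same at both mobility levels):

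pooled ratio = [Σ n·m·p / Σ n·m] ÷ [Σ n·(1−m)·p / Σ n·(1−m)]

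For a gap g, an overall share of 50% at 2:1 requires m(routine) = 0.5 − g/3 and m(novel) = 0.5 + 2g/3. The two denominators are then 2,400 each and cancel.

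| Mobile share, routine v novel | Prevalence, routine v novel | TB cases, mobile v less mobile | Pooled ratio |
|---|---|---|---|
| 43.3% v 63.3% | 3% v 4.5% | 87.2 v 80.8 | 1.08 |
| 43.3% v 63.3% | 3% v 6% | 102.4 v 89.6 | 1.14 |
| 38.3% v 73.3% | 3% v 6% | 107.2 v 84.8 | 1.26 |
| 43.3% v 63.3% | 3% v 2% | 61.9 v 66.1 | 0.94 |
| 50% v 50% | 3% v 6% | 96 v 96 | 1.00 |
| 43.3% v 63.3% | 3% v 3% | 72 v 72 | 1.00 |

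First row in full: mobile contacts number 3,200 × 0.4333 = 1,386.7 and 1,600 × 0.6333 = 1,013.3. Cases among them are 1,386.7 × 0.03 + 1,013.3 × 0.045 = 87.2. The less mobile number 1,813.3 and 586.7, with 1,813.3 × 0.03 + 586.7 × 0.045 = 80.8 cases. 87.2/80.8 = 1.08.

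Within each arm the ratio is 1.00 by construction, so adjusting for or stratifying by arm returns 1.00.

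**Step 3: size of a possible HIV pathway.** Let h be HIV prevalence in the less mobile and R the TB risk ratio for HIV. If the HIV-adjusted ratio is 1 and all of the 1.65 is mediation:

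total ratio = [1 + 1.65·h·(R−1)] / [1 + h·(R−1)]

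- h = 5%, R = 2: 1.0825/1.05 = 1.03
- h = 20%, R = 3: 1.66/1.40 = 1.19
- h = 20%, R = 5: 2.32/1.80 = 1.29
- h = 30%, R = 10: 5.455/3.70 = 1.47

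Both h and R are assumptions. The calculation also carries a ratio for migrants versus non-migrants in another province over to a midpoint split of daily kilometres or trips per year. It shows how far two reported ratios could differ; it does not estimate bias.

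**The case against.** The main counter-arguments, and what stands of each:

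- **The covariate list is open-ended.** True: its wording does not exclude arm. But it does not commit to arm either, and another outcome in the same section names it.
- **The arm mechanism needs two conditions.** This stands. If novel-arm prevalence is higher only because mobile people carry more TB, that is the association being estimated. Bias needs a prevalence difference at a given mobility level as well as a difference in mobile share. Age and sex differences between arms are already adjusted for.
- **A reader might infer that visits deferred by months distort both sites.** The plan does not support this. Section 6.1 gives routine and off-peak visits the same two-week booking window, so in Soshanguve any arm difference must come from who is at home.
- **A reader might infer that a worker met at a holiday visit is highly mobile by definition.** Not so. One measure is daily kilometres truncated at 50 km; the other is trips per year over 50 km, split near the midpoint. One trip need not place someone in the upper group on either.
- **A reader might take the doubled yield in Section 11.2 as doubled prevalence.** That figure is cases per index case, which more contacts alone could produce. The doubled prevalence in the table is an assumption.
- **A reader might infer that the background presents HIV as a consequence of migration.** Section 2.1 reports a link and a gradient with number of moves, and states no direction. Section 3 words the related aim as associations, so treating HIV as a confounder is defensible. What remains is that mediation is plausible and only one version of the ratio is planned.

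**Conclusion.** The point holds in limited form. As written, the mobility–TB model has no arm term, and the only population in which its ratio can be estimated includes contacts, whose enrolment depends on visit timing and therefore on arm. With no true effect, 50% highly mobile overall, 2:1 contacts and 3% routine-arm prevalence, the pooled ratio is about 1.08 to 1.26 for a gap of 20 to 35 percentage points in mobile share and novel-arm prevalence 1.5 to 2 times routine. It is about 0.94 for a 20-point gap with novel-arm prevalence of 2%, and exactly 1.00 if either factor is equal across arms. The gaps and novel-arm prevalences are assumed, so the documents establish that distortion is possible but not its size or direction. They do not show that a mobility association found in this trial would be spurious.

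On HIV, the supportable statement is that only an HIV-adjusted ratio is planned while HIV may be a mediator as well as a confounder. That calls for showing both estimates. It does not make the adjusted one wrong.

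**What to change.** Before analysis, amend secondary outcome 1 in Section 11.4 as follows:

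1. Replace index patients with contacts, or with individuals and an explicit definition of TB status, so that it agrees with Sections 8.1.2 and 11.1.
2. Add randomised arm as a covariate or stratum within each site, and report arm-specific ratios or a mobility-by-arm check.
3. Report each mobility ratio with and without HIV status, labelled as such, and state which association each describes.

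The cost is one covariate and one extra model per exposure, with slightly less precision and no new data. One limit remains: arm adjustment does not recover mobile people who were absent from visits within an arm, and the report should say so.

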- 4. **Off-peak contact investigation in urban Soshanguve and surrounding areas**. Study staff will perform contact investigation of TB cases diagnosed in study clinics in Soshanguve, throughout the year. Contact investigation will be performed during evenings and weekends.

[figure not shown]
Bioethics sub-study

We will perform a mixed-methods investigation of the ethics of household contact investigation for TB among participants from the parent study (both TB index cases and their household contacts) after they complete TB evaluation. This investigation will include a combination of focus group discussions (six groups of 10 participants each), in-depth interviews (24 interviews), and quantitative surveys (300 participants). Each of these investigations will follow a 2x3 factorial design, including equal representation of household contacts and index patients across

Version 5.0 13 October 2021

each of the three study districts.

Study Schematic

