8.1.2 Secondary Outcome Measures

- 1. The TB prevalence ratio, comparing highly mobile to less mobile individuals, measuring mobility on two scales (neighborhood/intra-urban and regional/intra-national).
- 2. Relative acceptability of each novel strategy, compared against routine contact investigation. We will create a continuous score from the acceptability interview questions (provided to a randomly selected 15% of the population), with a higher score indicating greater acceptability of the contact tracing strategy.
- 3. Feasibility of each strategy as the proportion of potentially eligible index cases for whom a household visit was conducted.
- 4. Relative fidelity of each novel strategy using a process checklist for each index case and household, including whether the household visit was offered and accepted, whether the visit was attempted, whether the visit was successful (i.e., enrolled at least one contact), whether symptom screening and sputum collection were completed and whether newly identified TB cases were notified and referred for treatment.
- Sustainability of each novel strategy by reporting the primary outcome and fidelity measures according to six-month time period over the course of the study.
- 6. Incremental cost-effectiveness ratio for each novel strategy. defined as (cost of contact tracing strategy 2 cost of strategy 1)/(effectiveness of strategy 2 effectiveness of strategy 1), where effectiveness is modeled as the number of disability-adjusted life years (DALYs) averted by the intervention. The primary cost-effectiveness measures will be the incremental cost per DALY averted using novel strategies (holiday and off-hours contact tracing) compared to routine contact tracing in each setting separately.

7. Experiences of inconvenience, attitudes toward confidentiality, motivation to participate, and preferences for disclosure, assessed through both thematic analysis of in-depth interviews and focus group discussions and quantitative analysis of discrete choice experiments and best-worst scaling.

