- 2. TB strain relatedness using maximum likelihood transmission trees. Along with standard genetic thresholds (i.e. SNP differences of <5) for assessing whether strains are related by transmission, we will construct a maximum-likelihood phylogenetic tree using RAxML and other tree estimation packages. We will then employ a Bayesian approach to infer transmission.^{65,66} After separating the data into distinct putative transmission clusters using a probabilistic approach combining SNPs, timing, and location information, we will generate timed phylogenetic trees for each cluster using Bayesian Evolutionary Analysis Sampling Trees (BEAST).¹¹⁶ We will then use a stochastic, continuous-time Monte Carlo Markov Chain (MCMC) representing a branching transmission model. We will model within-host evolution of Mtb assuming a neutral coalescent process and generate transmission trees using an MCMC approach.^{65,67} We will weight candidate transmission trees based on likely or unlikely linkages (e.g., household contacts). This method integrates TB natural history, epidemiological, and WGS-derived phylogenetic data into a statistical modeling framework to draw probabilistic conclusions about the likelihood of transmission between persons. "Transmitters" will be defined as individuals from whom at least one secondary case most likely originated.
- 3. Relative acceptability of each novel strategy. We will create an acceptability score from the interview questions, with a higher score indicating greater acceptability of the contact tracing strategy. We will use multivariable generalized linear regression model with a suitable link to model the acceptability score, with the primary exposure of interest being each novel contact investigation strategy (i.e off-hours tracing in Soshanguve, holiday tracing in Limpopo), relative to standard contact investigation in each setting. Analyses will be stratified by site
- 4. Feasibility of each strategy as the proportion of potentially eligible index cases for whom a household visit was conducted. We will also record all reasons why visits were unable to be conducted (e.g. could not find household, no one ever home, visit not conducted during expected off-peak period). Analyses will be stratified by site

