- 5. Relative fidelity of each novel strategy using a process checklist for each index case and household, including whether the household visit was offered and accepted, whether the visit was attempted, whether the visit was successful (i.e., enrolled at least one contact), whether symptom screening and sputum collection were completed and whether newly identified TB cases were notified and referred for treatment. We will model fidelity as a binary outcome, using log-binomial regression, with the primary exposure of interest being novel versus standard contact investigation (separately in each setting), adjusting for potential confounders (for example, socio-demographic and clinical factors) and enrollment site as with the acceptability outcome and robust standard errors for multiple outcomes per household. Analyses will be stratified by site

- 6. Sustainability of each novel strategy will be accomplished by incorporating an indicator variable for the six-month time windows of the study period into the multivariable regression models of acceptability and fidelity outcomes described above, and evaluating for interactions between this time window indicator and the primary exposure variable (i.e. investigation arm).

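### The listed fidelity items leave out whether the visit fell in its allocated time window, although timing is what separates the arms

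*Combined protocol and SAP*

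**What the plan says.** In each setting Section 4 separates the arms by when the household is visited.

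- The comparator is "standard household contact investigation during business hours from 8 am to 4 pm Monday through Friday".
- For the urban novel arm, "Contact investigation will be performed during evenings and weekends".
- In the rural novel arm the visit is deferred to an Easter or Christmas holiday period.

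Section 11.4, secondary outcome 5, measures fidelity "using a process checklist for each index case and household, including whether the household visit was offered and accepted". The list continues with "whether the visit was attempted, whether the visit was successful (i.e., enrolled at least one contact), whether symptom screening and sputum collection were completed", and ends with notification and referral of new cases. Section 8.1.2 (item 4) and Section 11.1 (item 5) give the same items, for example "whether the visit was successful (i.e., enrolled at least one contact").

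On analysis, Section 11.4 states: "We will model fidelity as a binary outcome, using log-binomial regression". It adds robust standard errors for multiple outcomes per household. It does not say which items, in what combination, make a household faithful.

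Visit timing appears in two other outcomes. Under feasibility (Sections 11.1 and 11.4), one example of a reason why a visit could not be carried out is "visit not conducted during expected off-peak period". Under acceptability (Section 11.1), one person in a 15% sample of visited households is asked, among other things, how acceptable the visit timing was.

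Sustainability reports the primary outcome and the fidelity measures by six-month period (Sections 8.1.2 and 11.1). Section 11.4 adds arm-by-period interactions in the acceptability and fidelity models.

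**The concern.** An outcome called fidelity of a novel strategy should show whether the novel element was delivered. Here that element is timing, yet every listed item applies equally to any household visit at any hour. Taken as listed, the comparison between arms measures how completely visits were carried out, not whether they took place when the allocation required.

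Two things are at stake. First, slippage of novel-arm visits into ordinary hours, or of routine visits into evenings, would not register in the listed fidelity items, and neither would a gradual drift over the 2.5 years of enrolment. Second, such slippage pulls the arms together on the primary outcome. A reader who sees a ratio below the twofold benchmark of Section 11.2 would look to fidelity to learn whether the strategy worked less well than hoped or was delivered at the wrong time. The listed items do not answer that.

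**Working it through.** **1. The listed items applied to off-window visits.** Take an off-peak household visited at 10 am on a Tuesday, a holiday household visited outside the holiday, and a routine household visited on a Saturday. In each, suppose that a contact is enrolled, screening and sputum collection are done, and any new case is notified and referred.

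| Listed item (8.1.2, 11.1, 11.4) | Answer in all three cases | Depends on the window? |
|---|---|---|
| Offered and accepted | yes | no |
| Attempted | yes | no |
| Successful (at least one contact) | yes | no |
| Screening and sputum completed | yes | no |
| New cases notified and referred | yes, or none to refer | no |

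No listed item separates these visits from correctly timed ones. Whether they count as faithful then depends on unlisted items and on a scoring rule that the plan does not give.

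**2. Sustainability.** The interaction of arm with six-month period is fitted to the fidelity outcome. If the outcome carries no timing item, the interaction cannot detect a change in timing.

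**3. Feasibility.** The numerator is index cases for whom a household visit was conducted, with no condition that it fell in the window. The off-peak example sits among reasons for visits not carried out, and no holiday equivalent is named. Whether an off-window visit is conducted or not conducted is left open.

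**4. Can the window be derived?** Not yet, for either novel arm.

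- Off-peak: the opening of Section 4 calls the approach evening-time, while the arm definition adds weekends. Routine visits end at 4 pm, but off-peak visits have no stated start, so a 4:30 pm weekday visit belongs clearly to neither arm.
- Holiday: Section 4 gives a three-week Easter period for cases diagnosed from January 1. The randomization text in Section 11.2 gives a two-week Easter holiday for patients enrolled from February 1. Length, start date and reference event (diagnosis or enrolment) all differ.

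**5. Illustration of size.** The plan states no fidelity figure to reproduce. From Section 11.2: means 0.06 (routine) and 0.12 (novel), 1600 and 800 index cases per setting, coefficient of variation 0.68. Assumptions: a share c of novel-arm households is seen off-window and yields the routine 0.06; alpha is 0.05 two-sided, which the documents do not state.

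Novel mean m = (1 − c) × 0.12 + c × 0.06 = 0.12 − 0.06c; ratio = m / 0.06.

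For c = 0.25: 0.75 × 0.12 + 0.25 × 0.06 = 0.105, and 0.105 / 0.06 = 1.75.

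Power was computed in two ways: (a) a two-proportion comparison; (b) Φ(|m − 0.06| / SE − 1.96), with SE² = v(0.06)/1600 + v(m)/800 and v(x) = x + (0.68x)².

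| c | Novel mean | Ratio | Power (a) | Power (b) |
|---|---|---|---|---|
| 0 | 0.120 | 2.00 | 0.998 | 0.990 |
| 0.25 | 0.105 | 1.75 | 0.967 | 0.924 |
| 0.50 | 0.090 | 1.50 | 0.762 | 0.672 |
| 0.67 | 0.080 | 1.33 | 0.459 | 0.389 |

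The first row is in line with the plan's power of above 0.99: (a) agrees, and (b) lies at that boundary.

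**The case against.** The strongest reply has four parts.

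- **The list is open.** All three places introduce the items as examples of what the checklist includes, and the form itself is not in the documents. This stands. A reader might infer that the trial never records visit timing; the documents do not support that, only that no listed item does so.
- **There is no scoring rule.** A reader might infer that a novel-arm household seen in business hours automatically earns full fidelity, so that fidelity could read 100% with no visit in the window. That presumes a composite built from the listed items alone. The reference to multiple outcomes per household fits separate modelling of each item at least as well. Such a score is possible but not stated.
- **Feasibility may catch part of it.** If an off-peak household not reached in its window is logged as not visited, the failure is visible there. This is a fair reading for the off-peak arm, and the reasons given are only examples. But nothing in the text confirms it, and the feasibility numerator carries no window condition.
- **Compliance is monitored.** Sections 13 and 15.6 describe daily oversight, form review, field visits and quarterly checks, and Section 10 refers to a manual of procedures that is not available here. These may pick up individual off-window visits, but they are not described as giving a measure by arm or period.

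The acceptability question does not fill the gap, because it asks for an opinion on timing and does not record whether the window was kept.

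**Conclusion.** The point holds as a gap in one secondary outcome and in the sustainability analysis that uses it. The fidelity items listed in three places omit the allocated window, the binary rule is undefined, and off-window visits can therefore be counted as faithful in any arm. The change is worth making because it alters what the fidelity outcome can show.

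The size is unknown, since the documents give no off-window share. Under the stated assumptions, 25% off-window visits reduce the ratio from 2.0 to 1.75 and 50% reduce it to 1.5. A reader might infer that undetected slippage would produce a null primary result. At 25% the illustration does not show that, because power remains about 0.92 to 0.97; the consequence is attenuation. Power falls to 0.67 to 0.76 only at 50%. Nor do the documents show that a null result could never be explained, since feasibility reasons and monitoring may reveal some timing failures. The primary analysis does not use the fidelity outcome and is not affected by how it is defined.

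**What to change.** 1. In Sections 8.1.2, 11.1 and 11.4, add a fidelity item: visit started within the allocated window (yes/no), derived from the recorded date and start time of each visit in all four arms.
2. Report this item on its own, by arm and by six-month period, and include it in any composite.
3. State how the checklist items form the binary outcome: one composite with a named rule, or a separate model for each item.
4. State whether an off-window visit counts as conducted in the feasibility numerator, for the holiday arm as well as the off-peak arm.
5. So that the item can be derived, use one off-peak definition (days and clock times) throughout Section 4. Reconcile the Easter period, its start date and its reference event between Section 4 and the randomization text in Section 11.2.

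The cost is protocol wording and one derived field in the electronic form. Reported fidelity may be lower once timing counts. Sample size and the primary analysis do not change.
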